Check for Adverse Events (5 minutes): At the Week 12 Visit, study staff will query the participant for any new health conditions that may have arisen since the Baseline Visit. Adverse event information will be collected and recorded as described in section K. Assessment of Subject Safety and Development of a Data and Safety Monitoring Plan below.

Acceptability surveys (30 minutes): Participants will complete 2 acceptability surveys at the 12 weeks (\pm 2 weeks). The first survey is a structured survey using 5-point Likert Scale (domains: affective attitude (how an participant feels about the MIND+SOUL intervention), burden (perceived amount of effort required to participate in the MIND+SOUL intervention), ethicality (extent to which the intervention has good fit with the participants value system), perceived effectiveness (extent to which the intervention is perceived as likely to achieve its purpose), and self-efficacy (participants confidence that they can perform the behaviors required to participate in the intervention). The second survey is a satisfaction with MIND+SOUL diet survey using a visual analog scale.

Post Intervention

Focus Group: Upon completion of cohort 1 and cohort 2 a subset of participants will participate in one of two focus group discussions to further capture feasibility and acceptability of the MIND+SOUL intervention. We will hold two 30-minute virtual semi-structured focus group discussions (n=2-3 participants per focus group) to capture feasibility and acceptability of MIND+SOUL intervention. Focus group participants will receive a \$25 Visa gift card for their participation.

	Baseline Visit (-30 Days)	Week 1-Week 6 (Day 0)	Week 7-Week 11	Week 12 Visit (+/- 2 weeks)
Informed Consent	X			
Urine pregnancy test, as needed	X			
Medical History/ Current medications	X			
Blood Pressure	X			X
Verification of Eligibility	X			
DXA Scan	X			X
Height / Weight/Waist circumference	X			X
Blood Draw	X			X
NHANES Dietary Screener Questionnaire	X			X
Skin Carotenoid Content	X			X
NIH Toolbox Cognitive Battery	X			X
Acceptability Surveys (structured survey and Visual Analog Scale)				X
Adverse Event Check				X
Skill Building Health Education/Cooking Classes 1x week		X		
Health Coaching 2x Month		x	x	

Testing Results

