Research results will be shared with the community through a powerpoint or poster presentation at a conference and via a letter with a summary of study findings, which will be mailed to participants at the end of the study. Further, study findings will be posted on social media outlets such as Facebook and Twitter. To sustain a research relationship with the AA community we plan to continue to pursue collaborative projects aimed specifically towards focusing on the needs for the community. Upon completion of this project we plan to expand this project on a larger scale by designing an AA culturally MIND+SOUL diet intervention for implementation as a future R01 scale clinical trial.

K. Assessment of Subject Safety and Development of a Data and Safety Monitoring Plan

1. Elements of the plan include:

- a. **Persons/groups who will review the data (study team; independent safety monitor):** PI: [name], Medical Monitor: [name], and independent safety monitor
- b. **Plan for safety monitoring and review:**

Adverse Event Definitions and Collection

In this trial, an adverse event (AE) is defined as any untoward or unfavorable medical occurrence in a human subject participant, including any abnormal sign, symptom, or disease, temporally associated with the participant's involvement in the research, whether or not considered related to participation in the research.

A serious adverse event (SAE) is defined as any adverse event that results in:

- Death
- Life-threatening even, a condition that places the study participant at immediate risk of death if they do not seek medical treatment
- Inpatient hospitalization, or prolongation of existing hospitalization
- Permanent disability, defined as the interruption of a study participant's ability to conduct normal life functions

AE's will be collected from the time of consent until the final study visit and will be recorded on an Adverse Event Report Form. At each study visit, study staff will query the participant for any new AE's that may have occurred since the last study visit and will check on the status of any AE's that have not previously resolved.

Adverse Event Assessment

A qualified study clinician will assess all AE's for severity, causality, and expectedness. This assessment will be documented with the medical monitor's signature and date.

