The PI will review all AE assessments and will follow up to obtain any further information necessary prior to approving the report. PI approval of the AE report will be indicated with her signature and date.

Severity will be assessed using the following guidelines:

- Mild-The adverse event may or may not be noticeable to the participant and does not significantly impact the participant's ability to complete activities of daily living (ADL's).
- Moderate- The adverse event is noticeable and causes some inconvenience and impact on the ability to complete ADL's.
- Severe-The adverse event has a very significant impact on the participant's ability to complete ADL's.

Causality, or relatedness to study intervention or procedures, will be categorized as:

- Definitely Related: The adverse event is clearly related to the study intervention / procedure – i.e., an event that follows a reasonable temporal sequence from administration of the study intervention, follows a known or expected response pattern to the suspected intervention, that is confirmed by improvement on stopping and reappearance of the event on repeated exposure and that could not be reasonably explained by the known characteristics of the subject's clinical state.
- Probably Related: The adverse event is more likely than not attributable to study intervention or procedures. i.e While other causes of the event may be possible, the temporal relationship of the event to the study intervention or procedure and other factors lead to the conclusion that the most likely cause is the study intervention/procedure.
- Possibly Related: An adverse event that follows a reasonable temporal sequence from administration of the study intervention and follows a known or expected response pattern to the suspected intervention, but that could readily have been produced by a number of other factors.
- Not Related: The adverse event is clearly not related to the study intervention /procedure - i.e., another cause of the event is most plausible; and/or a clinically plausible temporal sequence is inconsistent with the onset of the event and the study intervention and/or a causal relationship is considered biologically implausible.

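### Both acceptability surveys and the only scheduled post-baseline adverse event query sit at Week 12; no exit survey, reason-for-leaving item or interim adverse event question is described

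*Combined protocol and SAP*

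**What the plan says.** **Acceptability.** Sections I.A and V.B make acceptability, with feasibility, the primary outcome. It is measured after the intervention by two online REDCap surveys. Section II.E fixes the time: "Participants will complete 2 acceptability surveys at the 12 weeks", with a window of 2 weeks either side. The schedule table marks the surveys in the Week 12 column only.

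**Other feedback.** Section II.E adds focus groups: "Upon completion of cohort 1 and cohort 2 a subset of participants will participate in one of two focus group discussions", with 2 to 3 people in each. Section I.A lists reasons for declining to take part among the feasibility measures, but not reasons for leaving.

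**Adverse events.** Section II.E says "At the Week 12 Visit, study staff will query the participant for any new health conditions that may have arisen since the Baseline Visit", and the table marks the check at Week 12 only. It then refers to Section II.K: "Adverse event information will be collected and recorded as described in section K". Section II.K says "AE's will be collected from the time of consent until the final study visit and will be recorded on an Adverse Event Report Form" and "At each study visit, study staff will query the participant for any new AE's that may have occurred since the last study visit". Section II.E provides for two study visits, baseline and Week 12.

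**Contacts in between.** Section II.B describes six weekly classes and six bi-weekly coaching calls. No adverse event question is assigned to either.

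**Leaving early.** Section II.D.3 states that there are no withdrawal or termination criteria, and Section II.B expects every participant back at 12 weeks. No exit contact is described.

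**The concern.** Section II.C justifies the three cohorts of 10 by the chance to revise the intervention between them and so improve feasibility and acceptability. People who leave and do not come back are among those best placed to say what needs revising. Section I.B itself names cost, access, food preference and taste as reasons for poor adherence to earlier diets. Followed as written, the schedule surveys only those still reachable at Week 12. Retention figures will show how many left, not why. If non-returners liked the diet less, which is likely but not certain, the survey results will look too favourable.

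The safety question is separate. Section II.F anticipates gastrointestinal symptoms, some of which may be brief. Early ones may be forgotten, or poorly dated, by Week 12, and the causality grades in Section II.K depend on timing. The report to the safety monitor after each cohort can include what Week 12 attenders recall, but only volunteered events for anyone who does not return. A quarterly summary falling mid-cohort would likewise hold only volunteered events for that cohort.

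**Working it through.** The plan gives no figure to reproduce here. The check is of the schedule, followed by simple arithmetic.

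**1. Number of solicited adverse event queries after baseline.** Section II.K ties the query to study visits, and Section II.E has two visits. So 2 − 1 = 1 query follows baseline, at Week 12. The other contacts are 6 classes + 6 calls = 12 per person, none with an assigned adverse event question.

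**2. Time from diet start to that query.** Inputs: Week 12 ± 2 weeks, and baseline up to 30 days before diet start (Section II.E).
- Week 12 counted from Day 0, as the schedule table implies: 12 − 2 = 10 to 12 + 2 = 14 weeks (70 to 98 days). Recall back to the baseline visit can then reach 98 + 30 = 128 days, or 18.3 weeks.
- Week 12 counted from the baseline visit: the earliest is (70 − 30)/7 = 5.7 weeks after diet start. The latest is still 14 weeks, when baseline and diet start coincide.
- With a question at each coaching call: 12 weeks / 6 calls = about every 2 weeks.

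**3. What the focus groups could cover.** 2 groups × 2 to 3 people = 4 to 6 people in total, after cohorts 1 and 2 only. They are not described as including leavers.

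**4. Illustration of missing surveys.** The number missing, m, is an assumption. For any proportion among all 30 enrolled, the worst-to-best range has width m/30. For a mean Likert score, assumed to run from 1 to 5, it has width 4m/30.

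| m missing (assumed) | Proportion, m/30 | Likert mean, 4m/30 |
|---|---|---|
| 0 | 0 points | 0 |
| 3 | 10 percentage points | 0.4 |
| 6 | 20 percentage points | 0.8 |
| 9 | 30 percentage points | 1.2 |

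Example: if 24 of 30 are surveyed and 22 of them respond favourably (both assumed), the share among all enrolled lies between 22/30 = 73% and (22 + 6)/30 = 93%. In one cohort of 10, each missing survey adds 1/10 = 10 percentage points.

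These widths hold for any survey with missing answers and show no bias particular to this trial. The plan's 80% figure concerns completion of the intervention, not Week 12 attendance, so it does not establish that six surveys would be missing.

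**The case against.** A reader might infer that the views of everyone who leaves early are lost. The documents do not support that. All participants are expected back at 12 weeks, nobody is removed for stopping the diet, and the surveys are online, so a clinic visit is not strictly needed to answer them. A focus group could also include a leaver. The gap concerns people who do not return, and some of those will not answer an exit survey either.

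A reader might also infer that adverse events are captured only at Week 12. Section II.K collects them from consent, and its reporting clocks start when the investigator learns of an event, so reports between visits can be recorded. Participants have 12 staff contacts at which to volunteer one. Mild symptoms already listed as risks would usually not meet the expedited IRB criteria, which cover unexpected events. What is absent is solicitation between visits.

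Two further limits stand. The plan states no dropout rate and no acceptability threshold, so no documented decision is shown to change at 10, 20 or 30 points. The survey attachments and the Adverse Event Report Form are not available, and the consent pages were removed; handling of leavers could appear there. The claim is therefore about what the protocol describes.

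None of this supplies a planned exit contact or an interim question. The timing of the surveys and of the query is explicit.

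**Conclusion.** The point holds in limited form. For participants who do not return at Week 12, the protocol plans no capture of their views, their reasons for leaving or solicited adverse events, in a trial built to learn between cohorts. For everyone, diet-related symptoms are first solicited 10 to 14 weeks after diet start if Week 12 counts from Day 0, or about 6 to 14 weeks if it counts from baseline.

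The size of any distortion in acceptability depends on how many people fail to return, which the documents do not predict; it is zero with full retention. The bounds above illustrate sensitivity and do not estimate bias. This is a worthwhile, low-cost improvement that is best made before the next cohort starts. It does not invalidate the design.

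**What to change.** 1. **Surveys.** Keep Week 12 for all who reach it. Send the two existing REDCap surveys, plus one reason-for-leaving item, to anyone who stops and will not attend Week 12. Report these responses separately from completers', because they rate a shorter exposure, and give the number missing by cohort. Best- and worst-case bounds for all enrolled are optional and need no new data.
2. **Adverse events.** Add one question, using the Section II.K definition, to each of the six existing coaching calls and at early exit. Record answers on the existing Adverse Event Report Form and mark both in the schedule table.
3. **Anchor.** State whether Week 12 counts from Day 0 or from the baseline visit.

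**Cost.** A minor amendment with no new visits. The calls add up to 6 × 30 = 180 brief queries; at an assumed 1 to 2 minutes each, that is 180 to 360 minutes, or 3 to 6 hours in total, plus one query per early exit. Coaches, who have no adverse event role in the plan now, need a short instruction. More events will probably be recorded, and each brings review work: "A qualified study clinician will assess all AE's for severity, causality, and expectedness", the medical monitor signs, and "The PI will review all AE assessments". The documents give no time for those steps. Some leavers will not respond, so the number missing must still be reported.

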Body Composition (30 minutes): At baseline and 12 weeks (\pm 2 weeks), dual energy x-ray absorptiometry (GE Lunar iDXA) will be used to determine fat-free mass, fat mass, and percent body fat. DXA uses very low X-ray doses (0.02mREM) to detect changes in body composition on the order of 1.6-3.8%. Body weight, height and waist circumference will be recorded at baseline and at the 12 week mark (\pm 2 weeks). Weight will be obtained using a digital scale (\pm 0.1 kg; Befour Inc model #PS6600, Saukville, WI) and height will be measured using a stadiometer (Model PE-WM-60-84, Perspective Enterprises, Portage, MI). Body mass index (kg/m²) will be calculated. Waist circumference will be obtained using a calibrated tape.²¹

Dietary Screener Questionnaire (30 minutes): Nutritional health status change will be measured using the NHANES Dietary Screener Questionnaire administered by study personnel.

Skin Carotenoid Content (10 minutes): is a validated, biomarker of fruit and vegetable intake.²⁴⁻²⁶ The "Veggie meter" (Longevity Link Corporation) uses Resonance Raman spectroscopy to non-invasively measure skin carotenoid content. Three measurements will be taken on the fingertip and averaged (total time ~1 minute) by study personnel.

Cognition (30 minutes): Participants will complete a cognitive measurement session at the KU ADRC at the baseline and at the 12-week mark. The NIH Toolbox to assess the following domains: memory, language, reading, vocabulary, processing speed, and executive function.² Specifically the following tests will be administered: NIH-TB List Sorting Working Memory Test, NIH-TB Picture Vocabulary Test,

NIH-TB Oral Reading Recognition Test, and the NIH-TB Pattern Comparison Processing Speed Test, and NIH-TB Flanker Inhibitory Control and Attention. Test will be administered by a psychometrician.

Visit 2 – 12-week Evaluation

Estimated duration: 2.5 hours

At 12 weeks (\pm 2 weeks), participants will return to complete blood draw, blood pressure, DXA scan for body composition, height, weight, waist circumference, dietary screener questionnaire, skin carotenoid assessment, cognitive testing, a check for adverse events, and survey completion (acceptability surveys).

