The participant may be given a copy of their results related to their blood pressure, blood draw results, and body composition if they request it. The data will not be reviewed by the research team or a physician for the presence of clinically relevant abnormalities.

F. Risk/benefit assessment:

1. **Physical risk**
 - a. Blood draw: Participants May feel soreness, swelling, and bruising at the puncture site during the blood draw. This should go away within a day. Good clinical practice guidelines will be followed for biospecimen sampling.
 - b. DXA: There is always a slight chance of cancer from excessive exposure to radiation. However, given the small amount of radiation used in medical imaging, the benefit of an accurate diagnosis far outweighs the associated risk.
 - c. Food consumption: There is a chance that participants may experience gastrointestinal symptoms when consuming foods on the MIND+SOUL diet including but not limited to: nausea, vomiting, diarrhea, acid reflux, heartburn, indigestion, bloating/excess gas, hiccups, halitosis, cramping, abdominal pain, irritable bowel syndrome, constipation, change in bowel movements, and hemorrhoids, gallstones.
2. **Psychological risk.** There is minimal risk for psychological distress due to the nature of the research topic.
3. **Social risk.** There is minimal risk due to the nature of the research topic.
4. **Economic risk.** There is minimal risk due to the nature of the research topic. Participants

will receive up to \$50 worth of groceries each week (\$600 total) for 12 weeks during the study to offset the cost of healthy foods. Focus group participants will receive a \$25 Visa gift card for their participation.

5. Potential benefit of participating in the study

- a. Individuals participating in this study may feel empowered and valued as part of Alzheimer's prevention in the African American community
- b. To the field of Alzheimer's prevention, community participation of this study will help guide future research in the development of culturally appropriate dietary intervention strategies aimed to reduce the risk of cognitive decline specifically for African Americans

G. Location where study will be performed:

Laboratory tests, educational sessions, and skill-building health education/cooking classes, will take place at the KU ADRC. Counseling sessions will take place via Zoom.

H. Collaboration (with another institution, if applicable):

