Expectedness refers to the whether the AE is anticipated based on current knowledge of the nature, severity, and frequency of the risks of the study intervention, as defined in the protocol and in the informed consent form. Thus, an event may be listed as a known potential risk, but if the event occurs in a more severe intensity or occurs more frequently than what is known, the event would be considered unexpected.

Adverse Event Reporting

The PI will ensure that all AE's that meet reportability criteria will be reported to the IRB within the expedited IRB-specified timeframe. The KU IRB requires reporting of AE's (whether serious or non-serious) that are determined to be related or probably related to study participation and that were unexpected. The timeframe for reporting AE's/ SAE's that meet these criteria is within five working days of the PI learning of the event. An exception to this timeframe is the reporting of deaths that are determined to be related or probably related to study participation. These must be reported within 24 hours by phone or email, with a full adverse event report submitted within five working days.

Any SAE that is related or probably related to study participation and that is unexpected will also be reported expeditiously to the NIA program officer and to the independent safety officer, within 48 hours of knowledge of the SAE. However, SAE's that result in death that are determined to be related to the study will be reported to the NIA program officer within 24 hours of learning of the event.

A summary of all AE's/ SAE's will be reported to the NIA program officer on a quarterly basis. The PI and medical monitor will also review all AE's/ SAE's on quarterly basis as described below in the Data and Safety Monitoring Plan.

Data and Safety Monitoring Plan

The data and safety monitoring plan consists of oversight by an independent safety monitor.

At the conclusion of each cohort of the study intervention, the study team will provide a report to the independent safety monitor detailing all AE's that have occurred to date. Following the review of safety data, the safety monitor will document his assessment of safety and his determination to: 1) continue the study without any modifications, 2) continue the study, but

only with additional monitoring or other specified modifications to the protocol or 3) discontinue the study due to safety issues.

III. Subject Participation

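### No step takes a high Week 12 blood pressure reading to the participant, the medical monitor or adverse event assessment, and two sentences in the plan point away from doing so

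*Combined protocol and SAP*

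**What the plan says.** **Results.** Testing Results, near the end of II.E, lets participants have a copy of their blood pressure, blood draw and body composition results on request. The next sentence reads: "The data will not be reviewed by the research team or a physician for the presence of clinically relevant abnormalities". Section III.E says that no information on cardiometabolic health is conveyed to the participant.

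**Measurement.** At Week 12, "participants will return to complete blood draw, blood pressure, DXA scan for body composition" and the other assessments (II.E, Visit 2). The limit of 165 mmHg systolic or 95 mmHg diastolic appears only in exclusion (g) of II.D.2, as a baseline criterion that allows a further attempt that day or another day. II.B and III.B repeat the check but label it (f).

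**Adverse events.** At Week 12, "study staff will query the participant for any new health conditions that may have arisen since the Baseline Visit" (II.E, Check for Adverse Events). Section II.K describes a similar query at each visit. It defines an adverse event as "any untoward or unfavorable medical occurrence in a human subject participant, including any abnormal sign, symptom, or disease", linked in time to taking part. It says that adverse events "will be collected from the time of consent until the final study visit and will be recorded on an Adverse Event Report Form".

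**Oversight.** After each cohort, "the study team will provide a report to the independent safety monitor" that sets out the adverse events to date. Under Adverse Event Reporting, "The PI and medical monitor will also review all" adverse events each quarter.

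**The concern.** High blood pressure is one of the qualifying risk factors, and people may enter with readings up to 165/95. The protocol treats a reading above that as reason to keep someone out. It names no action if the same person exceeds it after 12 weeks on the diet.

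Raised blood pressure often causes no symptoms, so asking about new health conditions is a poor way to find it. This is more so when the participant has not been told the reading.

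Two things are at stake. The participant may leave the last visit unaware of a reading that needs follow-up. The safety monitor, who decides after each cohort whether to continue, modify or stop, may work from a report that omits it, although the measurement was made at the same visit as the adverse event check.

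**Working it through.** The plan gives no figure on this point, so the main check sets its sections side by side.

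**1. Is a Week 12 reading compared with a limit?** Exclusion (g) ties 165/95 to the baseline visit. The schedule of events marks eligibility verification at baseline only. II.B calls the 12-week evaluations identical to baseline, but that repeats the measurements. It does not turn an entry criterion into a safety rule. No Week 12 limit or repeat rule is written.

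**2. How would the reading become an adverse event?** The definition in II.K could cover it, and there is a general duty to collect and record. The described means of finding events, in II.E and II.K, is a question to the participant. Nothing tells staff to compare the measured value with anything or enter it on the form.

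**3. Would a later stage catch it?** Clinician assessment, the quarterly review and the cohort report are all described in terms of adverse events. A reading never recorded as one reaches none of them.

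**4. Would the participant know?** Under III.E, no. Under Testing Results, only by asking for a copy. The two sections do not agree.

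**5. Does the answer depend on how Testing Results is read?**

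| Reading of the sentence | Review of Week 12 blood pressure | Step to adverse event assessment | Participant told (III.E) |
|---|---|---|---|
| Covers all study data | Ruled out | None | No |
| Covers only copies given out | Not barred, not required | None | No |

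The last two columns are the same on both readings.

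**6. How selective would a 165 mmHg trigger be?** This bears on the fix and does not measure the problem. Assume no real change and readings that vary normally about the person's usual systolic value, with a between-visit SD of 8 to 12 mmHg (assumed; the documents give none). Then P(first reading > 165) = 1 − Φ((165 − usual)/SD).

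- Usual 150: 1 − Φ(15/8) = 3.0%; 1 − Φ(15/12) = 10.6%.
- Usual 155: 1 − Φ(10/8) = 10.6%; 1 − Φ(10/12) = 20.2%.
- Usual 160: 1 − Φ(5/8) = 26.6%; 1 − Φ(5/12) = 33.8%.

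A repeat at the same visit shares much of that visit's deviation. With an assumed same-visit correlation of 0.6 to 0.9 (bivariate normal) and a usual value of 160, 55% to 81% of first exceedances would again be above 165. If a repeat on another day is independent of the first, 27% to 34% would be.

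**7. Is there time?** The itemised Week 12 times in II.E are blood draw 10, blood pressure 10, body composition 30, dietary screener 30, skin carotenoids 10, cognition 30, adverse event check 5 and surveys 30. They sum to 155 minutes against a stated 2.5 hours (150 minutes). A repeat adds 10 minutes, or 10/150 = 6.7%. If all 30 participants needed one, the total would be 300 minutes.

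**The case against.** The best case against the point is that Testing Results concerns only what is handed to participants. The sentence follows directly on the offer of a copy. A blanket ban cannot be meant, since staff check baseline blood pressure and the PI confirms eligibility (II.B), and II.K lists people who review the data. On this view section II.K does the work: an abnormal sign is an adverse event, events must be recorded until the final visit, and the participant query is not said to be the only route. In a 30-person diet pilot, leaving the trigger to clinical judgement is a defensible choice.

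Much of this stands. A reader might infer that the plan forbids anyone to look at blood pressure for safety, or stops staff recording a high value. The documents do not support that, for the reasons just given. What remains is that permission to record is not an instruction, the one sentence on reviewing results points the other way, and III.E withholds the result on any reading.

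Three further objections are fair. First, the measurement methods cited in II.E (the NHANES protocol and American Heart Association recommendations) may include a step for high readings; they are not supplied, so this cannot be checked. Second, a Week 12 reading comes at the end of that person's intervention. It can inform later cohorts and the person's own care but cannot change their time on the diet, and no planned cohort follows the third. Third, one high reading proves little.

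**Conclusion.** The point holds as a gap in the written procedure. Followed as written, the plan can leave a symptomless Week 12 reading above 165/95 unknown to the participant, the medical monitor and the safety monitor. It should be corrected. Confidence is medium because the key sentence is ambiguous.

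Its size cannot be stated. The documents give no frequency of such readings, and none is assumed. An upper confidence bound calculated from zero observed events would not supply it: that would describe what a count could show, not how many readings are missed.

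Two stronger inferences should be resisted. A reading above the limit is not in itself an adverse event or evidence that the diet did harm: readings vary, exclusion (g) itself allows another attempt, and two devices are named (Omron in I.A and II.B, DinaMap in II.E). Nor do the documents show that any event would in fact be missed, since staff remain free to record one. The conclusion rests on the text supplied and on there being no applicable step in the cited measurement procedures.

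**What to change.** 1. Except blood pressure from the no-review sentence in Testing Results and from the statement in III.E. The no-review sentence can stay for body composition and stored plasma.
2. At Week 12, measure blood pressure first, as II.B does at baseline, with one named device used at both visits. If the reading is above 165 systolic or 95 diastolic, repeat it at that visit or, as exclusion (g) allows, on another day. Tell the participant, and refer a reading that stays high to the medical monitor. The monitor judges whether it is an adverse event and, if so, it goes on the Adverse Event Report Form for the usual assessment. Exclusion (l) already works this way: a PHQ9 score triggers the medical monitor's judgement.
3. In each end-of-cohort safety report, give the number of Week 12 readings taken, the number referred and the number judged adverse events.

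The cost is about 10 minutes for each high first reading, in a visit whose itemised times already exceed its stated length, or a return trip if the repeat is on another day. Add a little medical monitor time, three counts per report and a short protocol amendment. Some referrals will be ordinary variation, which a same-visit repeat filters only partly. That is why the last step is clinical judgement and not automatic recording.
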